### **1.3.5 Aspirin safety**

Low dose aspirin is interesting as a potential therapy for reproductive disorders because it has a demonstrated track record of both fetal and maternal safety. Randomized controlled trials (RCTs) in thousands of women showed no increase in adverse fetal sequelae in doses < 150 mg per day . In a meta-analyses of 22 studies, aspirin was not associated with an overall increase in the risk of congenital malformations . The same meta-analysis reported an increase in the risk of gastroschisis (OR 2.37; 95% CI, 1.44 – 3.88) in infants exposed to high-dose aspirin (325 mg per day) in the first trimester . This is biologically plausible since this malformation may be caused by vascular disruption of mesenteric vessels . Results were not confirmed in a recent population based case-control study  and the association between aspirin use and gastroschisis remains uncertain. Indeed, aspirin is often used empirically to treat infertility, recurrent miscarriage and Antiphospholipid syndrome (APS). Studies regarding safety are difficult to compare due to different doses, duration, and timing of aspirin use (with regard to pregnancy). Nonetheless, the majority of data indicates minimal fetal risk from *in utero* LDA exposure. In fact, a recent study noted that LDA was actually associated with a reduction in neurobehavioral difficulties in very preterm infants .

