### **4.3 Study Arm Assignment and Randomization**

Randomization of subjects was carried out to obtain a 1:1 allocation ratio between the treatment and placebo arms. Randomization was stratified by site. A computer algorithm generated by the data coordinating center (DCC) was created the random assignment to one of the treatment arms based on randomly permuted block design with randomly varied block sizes. The block sizes were known only by the DCC personnel. A total of 11,920 nulliparous women were to be enrolled (5960 per group) across seven sites in sub-Saharan Africa, South Asia, and Latin America. For balance, each site was to enroll no more than 25% of the total sample.

To study the possible effect of LDA on anemia, an ancillary study was to enroll at least 500 women to obtain hemoglobin measure at 4 weeks after initiation of therapy, with each site contributing at least 75 women to that sample. Some sites ultimately collected hemoglobin 4-weeks post randomization for all participants. In addition, hemoglobin measures were to be obtained from all women at 26 to 30 weeks gestational age. The analyses of this ancillary study will be described in a separate analysis plan document and will not be included as part of the primary study publication.

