## **7.5 Multiple Comparisons and Multiplicity**

There is only one formal hypothesis test for this study. As such, a statistical test will be conducted at a 5% type I error rate (two-sided) for the primary efficacy measure, and no adjustments for multiplicity will be made. All analyses of secondary outcomes are exploratory in nature; therefore, p-values and confidence intervals are provided for descriptive purposes only. All p-values provided for any baseline and demographic characteristics and safety parameters will be for descriptive purposes only. As such, unless otherwise specified, p-values presented will be on a per analysis basis, with no further control for multiple tests.

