### **10. SAFETY ANALYSIS:**

No formal safety analyses are planned as a part of this study, although rates of pregnancy complications identified by ultrasound will be summarized as will SAEs and hospitalizations. No formal hypothesis tests will be conducted, but descriptive p-values generated using Cochran-Mantel-Haenszel statistics with stratification by GN site will be generated.

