Hypertensive Disorders, N (%)				
GN01: DRC				
GN03: Zambia				
GN12: Kenya				
GN06: Guatemala				
GN08: Belagavi				
GN11: Nagpur				
GN09: Pakistan				
Small for Gestational Age				
GN01: DRC				
GN03: Zambia				
GN12: Kenya				
GN06: Guatemala				
GN08: Belagavi				
GN11: Nagpur				

Outcome Measure	Risk of Outcome			
	Placebo N = XXXX	Aspirin N = XXXX	RR (95% CI)	p-Value
GN09: Pakistan				
Perinatal Mortality				
GN01: DRC				
GN03: Zambia				
GN12: Kenya				
GN06: Guatemala				
GN08: Belagavi				
GN11: Nagpur				
GN09: Pakistan				
Preeclampsia				
GN01: DRC				
GN03: Zambia				
GN12: Kenya				
GN06: Guatemala				
GN08: Belagavi				
GN11: Nagpur				
GN09: Pakistan				
Eclampsia				
GN01: DRC				
GN03: Zambia				
GN12: Kenya				
GN06: Guatemala				
GN08: Belagavi				
GN11: Nagpur				
GN09: Pakistan				

*NOTE: Table contains outcomes summarize using MITT population as well as outcomes summarized using ITT population. Final table will clearly identify which population is used for each outcome. Birth weight will be summarized both including and excluding estimated weights. Footnotes will be included to describe p-value and RR is from unadjusted model that includes a site by treatment group interaction term. The p-value for the interaction term will also be presented.*

Table 6: Serious Adverse Event Summary

Variable	Placebo N (%)	Aspirin N (%)	Relative Risk RR (95% CI)	p-Value
Randomized, N				
Participants with at least one SAE 				
Maternal death  , N (%)				
Fetal loss after 20 weeks  , N (%)				
Fetal anomaly  , N (%)				
Antepartum hemorrhage  , N (%)				
Post-partum hemorrhage  , N (%)				
Preeclampsia/Eclampsia  , N (%)				
Upper GI bleeding  , N (%)				
Gastroschisis, N (%)				
At least one Other SAE  , N (%)				

The denominator for this table is any woman included in the safety population.

Table 7a: Summary of Protocol Deviations by Treatment Arm

Variable	Arm 1	Arm 2	Total
Randomized, N (%)	XXXX	XXXX	XXXX
At least one protocol deviation, N (%)	XXX (Y.Y)	XXX (Y.Y)	XXX (Y.Y)
Protocol deviations, N	XX	XX	XX
Study participant enrolled but did not meet inclusion criteria	XX	XX	XX
Study participant enrolled but met criteria requiring exclusion	XX	XX	XX
Study participant enrolled twice	XX	XX	XX
Medication card was lost or destroyed	XX	XX	XX
The study participant was incorrectly randomized	XX	XX	XX

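### SAP section 10 and Table 6 set no sparse-data rule for the serious adverse event rows, so with few events the printed p-value can understate the exact one and the relative-risk interval can be undefined

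*Combined protocol and SAP*

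**What the plan says.** SAP section 10 states that no formal safety analyses or hypothesis tests are planned. It then says "descriptive p-values generated using Cochran-Mantel-Haenszel statistics with stratification by GN site will be generated". SAP section 7.5 gives these values the same status: "All p-values provided for any baseline and demographic characteristics and safety parameters will be for descriptive purposes only".

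Table 6 in SAP section 14 has counts and percentages by arm, a relative risk with 95% confidence interval, and a p-value. Its rows include maternal death, fetal anomaly, upper GI bleeding and gastroschisis. On denominators: "The denominator for this table is any woman included in the safety population". Maternal mortality through 42 days also appears in Table 5a, whose note takes the p-value from a CMH test.

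SAP sections 7.1 and 10 and Table 6 name no exact test, continuity correction, minimum event count, relative-risk estimator or zero-event rule for these rows.

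Protocol section 3.5.1 lists these harms for specific monitoring. Protocol section 1.3.5 says a meta-analysis "reported an increase in the risk of gastroschisis" at high dose, and calls the association uncertain. Protocol section 2.8 notes that earlier studies did not assess safety in the developing world and makes safety monitoring a strong focus.

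**The concern.** One method is set for every row, from common events to those that may number a handful across seven sites. The CMH chi-square is a large-sample approximation. In some small tables its p-value is well below the exact probability, and a ratio cannot be given a standard interval when one arm has no events.

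At stake is how the trial presents the harms that its own protocol singles out. A chance imbalance in a row such as gastroschisis could be printed with a p-value just under 0.05 when the exact evidence is weaker. In a row with no events in one arm, the interval would be blank or meaningless. Because no formal safety test is planned, that interval is the main way a reader would judge how much harm the data leave open.

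**Working it through.** **Inputs.** SAP section 4.3: "A total of 11,920 nulliparous women were to be enrolled (5960 per group) across seven sites"; "Randomization was stratified by site"; allocation 1:1. The safety population is taken as about 5,960 per arm (assumption). The documents give no expected counts for these rows, so all splits below are illustrations.

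**The plan's own figure.** Section 10 and Table 6 state none, so only the arm size can be checked. For 8% against 6.4%, two-sided 0.05, 90% power and pooled variance:

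n = [1.960 × √(2 × 0.072 × 0.928) + 1.282 × √(0.08 × 0.92 + 0.064 × 0.936)]² / 0.016² = 5,483.

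5,483 / 0.92 = 5,960. Both match SAP section 6.1.

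**CMH with rare events.** Take a events in one arm and b in the other, 1:1 within site. The sum of observed minus expected is (a − b)/2 and the variance is about (a + b)/4, so chi-square ≈ (a − b)²/(a + b) on 1 df. The full site-stratified calculation with seven equal or unequal sites, and events spread out or all in one site, gives chi-square 4.00 to 4.01 and p = 0.045 to 0.046 for 4-0. The site layout does not matter.

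**Exact p.** Given the total, a is binomial with probability 0.5. For 4-0: 2 × 0.5⁴ = 0.125 (Fisher 0.1249).

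| Split | Chi-square | Uncorrected CMH p | Exact p |
|---|---|---|---|
| 3-0 | 3.00 | 0.083 | 0.250 |
| 4-0 | 4.00 | 0.046 | 0.125 |
| 5-0 | 5.00 | 0.025 | 0.063 |
| 6-0 | 6.00 | 0.014 | 0.031 |
| 7-1 | 36/8 = 4.50 | 0.034 | 0.070 |
| 9-2 | 49/11 = 4.45 | 0.035 | 0.065 |
| 11-3 | 64/14 = 4.57 | 0.033 | 0.057 |
| 12-4 | 64/16 = 4.00 | 0.046 | 0.077 |
| 14-5 | 81/19 = 4.26 | 0.039 | 0.064 |

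**How often.** For each total m, the conditional error rate sums the binomial (m, 0.5) probabilities of splits with uncorrected p < 0.05:

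- Above 5%: m = 4 (12.5%), 5 (6.3%), 8 (7.0%), 11 (6.5%), 14 (5.7%), 16 (7.7%), 19 (6.4%).
- Below 5%: every other total up to 20, from 0% at 1 to 3 events to 4.9% at 17.
- Unweighted mean over totals 1 to 11: 3.9%.
- Averaged over Poisson totals with means 2, 4, 6, 10 and 20: 1.4%, 4.1%, 4.7%, 4.4% and 5.2%.

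**Relative risk at 4-0.** With events in four sites, the Mantel-Haenszel numerator is 4 × 0.5 = 2 and the denominator is 0. The log-ratio variance divides by their product, so it is undefined. A Poisson log-link model with site terms gives a log ratio of about 21 with standard error about 13,000. The exact conditional lower limit uses 0.025^(1/4) = 0.398, so 0.398/0.602 = 0.66; the upper limit is infinite. Adding 0.5 to each cell gives 9.0 (0.48 to 167).

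**Risk scale at 4-0.** 4/5,960 = 6.7 per 10,000. The exact (Clopper-Pearson) intervals are 1.8 to 17.2 per 10,000 for 4 events, and 0 to 1 − 0.025^(1/5,960) = 6.2 per 10,000 for none. Both are finite.

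**The case against.** The strongest reply is that the SAP has already limited the consequence. It plans no formal safety test, labels these p-values descriptive, and prints counts by arm, so a reader sees 4 against 0 directly. No decision depends on p < 0.05. This stands and keeps the point minor. It does not make 0.046 a good description of evidence whose exact value is 0.125.

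A reader might infer three stronger things that the documents do not support.

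- *That CMH inflates false alarms across the safety table, or fails at every small count.* It does not. The test is discrete: anti-conservative at some totals and conservative at others, with an average near or below 5%.
- *That the trial will print 0.046 for a named harm.* The SAP specifies no CMH variant. With a continuity correction, 4-0 gives (4 − 1)²/4 = 2.25, p = 0.13, close to exact. No expected counts are given, so such a split may never occur. The gap is that neither the variant nor the zero-event handling is stated.
- *That an exact relative-risk interval would show how large a harm remains possible.* At 4-0 it runs from 0.66 to infinity. An upper bound needs the risk scale.

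Exact tests also lose sensitivity, which matters for harms. Over totals 1 to 11 the exact test's mean error rate is about 1.2%, and it cannot fall below 0.05 with five or fewer events. This stands as a cost.

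**Conclusion.** The point holds as a small, easily corrected gap. With no sparse-data rule, the usual uncorrected CMH p-value can understate the exact one in rows with few events, by nearly a factor of three at 4-0 and about a factor of two at 7-1. The standard relative-risk interval does not exist when one arm has no events.

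This rests on 1:1 allocation, about 5,960 women per arm, the uncorrected CMH, a Mantel-Haenszel or log-link relative risk, and illustrative event counts. The p-values do not depend on how events fall across sites. The primary analysis is unaffected; the consequence is confined to how rare named harms are presented in Table 6 and in the maternal mortality row of Table 5a.

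**What to change.** Add to SAP section 10, before unmasking, a rule for rows whose total falls below a pre-stated number of events, for example under about 20:

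1. Report the exact site-stratified (conditional) p-value in Table 6 and in the maternal mortality row of Table 5a.
2. Give counts with an exact or score interval for the risk difference, or exact risk intervals per arm, so that rows with no events in one arm still carry a finite bound.
3. Show the relative risk, with an exact interval, only where it is estimable.
4. Keep CMH for the other rows, and state whether it is continuity-corrected.

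An exact interval fits best beside an exact p-value. At 4-0 the score lower limit for the ratio is 4/1.96² = 1.04, which excludes no difference while the exact p is 0.125.

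The cut-off is a judgement. A limit near 12 would miss 11-3, 12-4 and 14-5, and isolated disagreements continue above 20: 15-6 gives 81/21 = 3.86, p = 0.0495, against exact 0.078. Fixing the number in advance matters more than its exact value.

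The cost is a few sentences and a standard exact option in the analysis software. Because exact p-values are conservative, the text should direct readers to the counts and intervals.

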### **11. INTERIM ANALYSES AND DATA MONITORING**

No formal interim efficacy analyses were planned nor conducted for the study. Because the study was planned with an enrollment period of 24 months with the duration between randomization and determination of study endpoint being 6 to 8 months, preliminary analyses indicated that all participants would have completed randomization well before sufficient data could be accumulated for an interim efficacy analysis.

While no formal efficacy analysis was planned, the Data Monitoring Committee (DMC) reviewed the study at periodic intervals, to evaluate whether any safety or study progress issues warrant possible study stopping. These periodic reviews were based on DMC reports prepared by the Data coordinating center, which included information on study enrollment rates and participant progress through the study, participant compliance with protocol-specified treatment regimens, protocol violations, adverse events, and efficacy outcomes. The focus of the DMC review was on monitoring participant safety and study progress/futility but data on treatment effectiveness was also presented to frame the DMC discussions on safety and futility.

The primary focus of the DMC was on the safety of study participants and the DMC monitored adverse events and side effects from LDA. All known associated side effects and specific obstetric or fetal concerns were considered reportable to the DMC.

The DMC also reviewed the study progress for study progress and futility, with futility for these analyses defined in terms of inability to achieve study enrollment goals. To effectively complete the study within the parameters defined by NICHD and the Global Network Steering Committee, the goal

of study was to complete enrollment in a 24-month period, and enrollment be completed within 30 months. Consequently, cumulative enrollment for the study should at worst case achieve a minimum of 20%, 40%, 60%, and 80% of total enrollment at the 6, 12, 18, and 24-month DMC reviews starting from the time the study is first opened to enrollment. Should the study have failed to achieve at least 90% of the cumulative target at any review, the DMC would have requested from the protocol committee an action plan for increasing enrollment that should be delivered to the DMC for review within a 1-month period. Should the DMC have considered the plan inadequate or should the plan not result in increased enrollment by the next review, the DMC would have considered recommending to the NICHD closing the study for futility.

## **12. CHANGES TO THE ANALYSES PLANNED IN THE PROTOCOL**

Additional sensitivity analyses beyond those included in the original protocol have been included in Sections 7.3 and 9 to account for loss-to-follow-up and to account for early pregnancy losses. Also, one secondary outcome variable has been modified and one secondary outcome variable has been added. The outcome of risk of preeclampsia or eclampsia has been modified to clarify that this outcome is the risk of a hypertensive disorder of pregnancy. This modification was made to clarify the true variable of interest, reflecting the data collection process used in the MNH registry. The outcome of preterm, preeclampsia has been added to the secondary outcome list to reflect additional research that was reported on this outcome after the study was launched.

#### **14. ATTACHMENTS**

Table 1	Participant Distribution
Table 2	Baseline Characteristics
Table 3	Patient Medication Compliance
Table 4	Reasons for Noncompliance
Table 5	Primary and Secondary Efficacy Outcomes
Table 6	Key Safety (SAE) Outcomes
Table 7	Protocol Deviations
Figure 1	Consort Diagram

Table 1. Participant Distribution

GN Site	Screened N	Consented N (%)	Eligible N (%)	Randomized N (%)	Analysis Population Membership N (%)				Withdrew consent N (%)	Study Terminations - N (%)		
					Safety	MITT	ITT	PP		Terminated	Participant moved away from study area	Investigator terminated participant
GN02: DRC												
GN03: Zambia												
GN06: Guatemala												
GN08: India (Belagavi)												
GN09: Pakistan												
GN11: India (Nagpur)												
GN12: Kenya												
Total												

NOTE: Analysis population membership % will be out of randomized.

Table 2: Baseline Characteristics – For ITT and MITT Populations

Variable	Placebo	Aspirin	Total
Randomized, N			
Maternal Age, N (%)			
< 20			
20-29			
> 29			
Median (P25, P75)			
Projected GA at Enrollment, N (%)			
6,0 - 7,6			
8,0 - 9,6			
10,0 - 10,6			
11,0-11,6			
12,0 - 13,6			
Median (P25, P75)			
Maternal Education, N (%)			
No formal			
Primary			
Secondary			
University+			
Maternal Height			
Mean (StdDev)			
Median (Min, Max)			
Maternal Weight			
Mean (StdDev)			
Median (Min, Max)			
BMI			

Variable	Placebo	Aspirin	Total
Mean (StdDev)			
Median (Min, Max)			
Number of Antenatal Care Visits			
Median (P25, P75)			
Delivery Attendant, N (%)			
Physician			
Nurse/Nurse midwife			
TBA			
Family/Self/Other			
Delivery Location, N (%)			
Hospital			
Clinic/Health Center			
Home/Other			
Delivery Mode, N (%)			
Vaginal			
C-Section			
Miscarriage			
MTP			

Table 3: Participant Medication Exposure and Compliance – For MITT and ITT Populations

Compliance/Exposure Parameter	Placebo (N = XXXX)	Aspirin (N = XXXX)
No Drug		
Gestational age at first dose (weeks)		
Mean (StdDev)		
Median (Min, Max)		
Gestational age at last dose (weeks)		
Mean (Std Err)		
Min, Max		
Total number of days doses taken		
Mean (Std Err)		
Min, Max		
Level of Adherence: N (%)		
0% – 30%		
30% – 50%		
50% – 70%		
70% – 90%		
>90%		
Level of Exposure: N (%)		
0% – 30%		
30% – 50%		
50% – 70%		
70% – 90%		
>90%		

*NOTE: Summaries of gestational age at first and last dose excludes individuals who never initiated treatment while such individuals are included in summaries of all other parameters.*

Table 3a: Medication Compliance by Site – MITT Population

GN Site	Enrolled N	Level of compliance					
		Total Dosed N	< 30% N (%)	30-50% N (%)	50-70% N (%)	70-90% N (%)	> 90% N (%)
GN02: DRC							
GN03: Zambia							
GN06: Guatemala							
GN08: India (Belagavi)							
GN09: Pakistan							
GN11: India (Nagpur)							
GN12: Kenya							

Table 4: Reasons for Medication Noncompliance – MITT Population

Measures of Non-Compliance	Placebo	Aspirin
Number of Biweekly Visits N		
Visits where pills not taken as instructed, N (%)		
Reasons for Noncompliance, N (%)		
Another person took pills		
Pills were lost		
Pills made me feel sick		
Forgot to take pills		
Travelled and did not bring pills		
Didn't understand instructions for pills		
Pills were destroyed		
Other		

Table 5a: Primary and Secondary Efficacy Outcomes

	Placebo N = XXXX	Aspirin N = XXXX	p-value	Unadjusted RR (95% CI)	Adjusted RR (95% CI)
Primary Outcome, N included					
Preterm Delivery, N (%)					
Secondary Efficacy Outcomes					
Hypertensive Disorders, N (%)					
Small for Gestational Age, N (%)					
Perinatal Mortality, N (%)					
Other Maternal Outcomes of Interest					
Vaginal bleeding, N (%)					
Antepartum hemorrhage, N (%)					
Postpartum Hemorrhage, N (%)					
Maternal mortality through 42 days, N (%)					
Late Abortion, N (%)					
Preterm Preeclampsia, N (%)					
Other Fetal Outcomes of Interest					
Preterm birth <34 0/7 weeks of pregnancy, N (%)					
Birth weight < 2500g, N (%)					
Birth weight < 1500g, N (%)					
Fetal Loss, N (%)					
Spontaneous abortion, N (%)					
Stillbirth, N (%)					
Medical Termination of Pregnancy (MTP), N (%)					

*NOTE: Table contains outcomes summarize using MITT population as well as outcomes summarized using ITT population. Final table will clearly identify which population is used for each outcome. Birth weight will be summarized both including and excluding estimated weights. Adjusted RR will not be presented in primary paper. Footnotes will be included to describe p-value is from CMH test as well as models used to obtain RR estimates.*

Table 5b: Primary and Secondary Efficacy Outcomes by Site

*NOTE: Table will also include fetal outcomes of interest.*

Outcome Measure	Risk of Outcome			
	Placebo N = XXXX	Aspirin N = XXXX	RR (95% CI)	p-Value
Preterm Delivery, N (%)				
GN01: DRC				
GN03: Zambia				
GN12: Kenya				
GN06: Guatemala				
GN08: Belagavi				
GN11: Nagpur				
GN09: Pakistan				
Hypertensive Disorders, N (%)				
GN01: DRC				
GN03: Zambia				
GN12: Kenya				
GN06: Guatemala				
GN08: Belagavi				
GN11: Nagpur				
GN09: Pakistan				
Small for Gestational Age				
GN01: DRC				
GN03: Zambia				
GN12: Kenya				
GN06: Guatemala				
GN08: Belagavi				
GN11: Nagpur				

Outcome Measure	Risk of Outcome			
	Placebo N = XXXX	Aspirin N = XXXX	RR (95% CI)	p-Value
GN09: Pakistan				
Perinatal Mortality				
GN01: DRC				
GN03: Zambia				
GN12: Kenya				
GN06: Guatemala				
GN08: Belagavi				
GN11: Nagpur				
GN09: Pakistan				
Preeclampsia				
GN01: DRC				
GN03: Zambia				
GN12: Kenya				
GN06: Guatemala				
GN08: Belagavi				
GN11: Nagpur				
GN09: Pakistan				
Eclampsia				
GN01: DRC				
GN03: Zambia				
GN12: Kenya				
GN06: Guatemala				
GN08: Belagavi				
GN11: Nagpur				
GN09: Pakistan				

*NOTE: Table contains outcomes summarize using MITT population as well as outcomes summarized using ITT population. Final table will clearly identify which population is used for each outcome. Birth weight will be summarized both including and excluding estimated weights. Footnotes will be included to describe p-value and RR is from unadjusted model that includes a site by treatment group interaction term. The p-value for the interaction term will also be presented.*

Table 6: Serious Adverse Event Summary

Variable	Placebo N (%)	Aspirin N (%)	Relative Risk RR (95% CI)	p-Value
Randomized, N				
Participants with at least one SAE 				
Maternal death  , N (%)				
Fetal loss after 20 weeks  , N (%)				
Fetal anomaly  , N (%)				
Antepartum hemorrhage  , N (%)				
Post-partum hemorrhage  , N (%)				
Preeclampsia/Eclampsia  , N (%)				
Upper GI bleeding  , N (%)				
Gastroschisis, N (%)				
At least one Other SAE  , N (%)				

The denominator for this table is any woman included in the safety population.

Table 7a: Summary of Protocol Deviations by Treatment Arm

Variable	Arm 1	Arm 2	Total
Randomized, N (%)	XXXX	XXXX	XXXX
At least one protocol deviation, N (%)	XXX (Y.Y)	XXX (Y.Y)	XXX (Y.Y)
Protocol deviations, N	XX	XX	XX
Study participant enrolled but did not meet inclusion criteria	XX	XX	XX
Study participant enrolled but met criteria requiring exclusion	XX	XX	XX
Study participant enrolled twice	XX	XX	XX
Medication card was lost or destroyed	XX	XX	XX
The study participant was incorrectly randomized	XX	XX	XX
The randomization assignment was revealed to study personnel, participant or both	XX	XX	XX
Other deviation	XX	XX	XX
Protocol Deviation Rate (N/Person Month), Mean (StdDev)	X.X	X.X	X.X

Table 7b: Summary of Protocol Deviations by Site

Variable	GN02	GN03	GN06	GN08	GN09	GN11	GN12
Randomized, N (%)	XXXX						
At least one protocol deviation, N (%)	XXX (Y.Y)						
Protocol deviations, N	XX						
Study participant enrolled but did not meet inclusion criteria	XX						
Study participant enrolled but met criteria requiring exclusion	XX						
Study participant enrolled twice	XX						
Medication card was lost or destroyed	XX						
The study participant was incorrectly randomized	XX						
The randomization assignment was revealed to study personnel, participant or both	XX						
Other deviation	XX						
Protocol Deviation Rate (N/Person Month), Mean (StdDev)	X.X						

Figure 1: Consort Diagram
